## **5.2 Randomization (Day 0)**

Randomization will be done using a random number table generated by the NIH pharmacy department. Twenty-two (22) subjects will be randomized initially to receive rifaximin 550 mg twice daily for 4 weeks and 22 subjects will be randomized to receive placebo one tablet twice daily for 4 weeks.

The following procedures and laboratory tests labs will be performed and/or obtained at Day 0:

### **General Procedures**

- Targeted history and physical examination as medically indicated
- Adherence counseling and pill counts
- Assessment of signs and symptoms
- Study product dispensing (subjects will be asked to initiate study drug the day after randomization is complete)

### **Safety Labs**

- CBC with differential, platelet count

- BUN, creatinine, electrolytes (including sodium, potassium, chloride, carbon dioxide/bicarbonate), liver function tests [including ALT, AST, bilirubin, SAP]
- Urine pregnancy test if applicable (of child bearing potential)

#### **Research Labs**

- Immunophenotyping to include a CD4 count and cellular markers of activation (including HLA DR, CD38, co-expression of HLA DR and CD38 on CD4 and CD8 cells)
- Single copy assay and HIV-1-RNA levels
- Soluble markers of inflammation (interleukin6 [IL6], highly sensitive C reactive protein [hsCRP], tumor necrosis factor [TNF $\alpha$ ], D-dimer)
- Markers of bacterial translocation (LPS, bacterial 16S rDNA/bacterial RNA, soluble CD14 [sCD14])

#### **Sample Storage**

- Every attempt will be made to collect stool for each study visit but due to logistical constraints, samples may not be collected at each study visit. Patients may obtain samples at home and bring to the visit if preferred.
- Sample storage
- An optional baseline colonoscopy with gut biopsy will be completed in the 30 days prior to randomization
- All subjects undergoing a colonoscopy at baseline will receive a follow up phone call within 2 business days of their colonoscopy to ensure their safety.

### **5.3 Treatment Phase Visits**

Subjects will undergo a total of eleven (11) study visits: two (2) screening visits, four (4) visits during the rifaximin dosing phase (Days 0, 7, 14, and 28); four (4) visits during the placebo dosing phase (Days 0, , 7, 14, and 28) and one (1) final visit (4 weeks after completion of both dosing phases). Between weeks 8-10 of the study (4 weeks on study treatment followed by a 4-6 week washout), all subjects will cross over to the other treatment arm. The Day 3 visits of the rifaximin and placebo phases of the study ARE OPTIONAL.

### **5.4 Treatment Phase 1**

#### **Day 3 (optional visit)**

##### **General Procedures**

- Targeted history and directed physical examination as medically indicated
- Adherence counseling and pill counts
- Assess signs and symptoms

##### **Safety Labs**

- Urine pregnancy test if applicable (of child bearing potential)

##### **Research Labs**

- CBC with differential
- Immunophenotyping to include a CD4+ count and cellular markers of activation (including HLA DR, CD38, co-expression of HLA DR and CD38 on CD4+ and CD8+ cells)
- Single copy assay & HIV-1- RNA levels
- Soluble markers of inflammation (IL6, hsCRP, TNF $\alpha$ , D-dimer)

### **Sample Storage**

- Stool storage for fecal microbiome analysis

### **Day 7 +/- 3days**

### **General Procedures**

- Targeted history and directed physical examination as medically indicated
- Adherence counseling and pill counts
- Assess signs and symptoms

### **Safety Labs**

- Urine pregnancy test if applicable (of child bearing potential)

### **Research Labs**

- CBC with differential
- Immunophenotyping to include a CD4+ count and cellular markers of activation (including HLA DR, CD38, co-expression of HLA DR and CD38 on CD4+ and CD8+ cells)
- Single copy assay & HIV-1- RNA levels
- Markers of bacterial translocation (LPS, bacterial 16S rDNA/bacterial RNA, sCD14)
- Soluble markers of inflammation (IL6, hsCRP, TNF $\alpha$ , D-dimer)

### **Sample Storage**

- Stool storage for fecal microbiome analysis
- Sample storage

### **Day 14 +/- 3 days**

- Targeted history and directed physical examination as medically indicated
- Adherence counseling and pill counts
- Assess signs and symptoms

### **Safety Labs**

- Urine pregnancy test if applicable (of child bearing potential)
- PT/INR

### **Research Labs**

- CBC with differential
- Immunophenotyping to include a CD4 count and cellular markers of activation (including HLA DR, CD38, co-expression of HLA DR and CD38 on CD4+ and CD8+ cells)
- Single copy assay & HIV-1- RNA levels
- Markers of bacterial translocation (LPS, bacterial 16S rDNA/bacterial RNA, sCD14)
- Soluble markers of inflammation (IL6, hsCRP, TNF $\alpha$ , D-dimer)

### **Sample Storage**

- Stool storage for fecal microbiome analysis
- Sample storage

### **Day 28 +/- 3 days**

- Targeted history and directed physical exam as medically indicated
- Adherence counseling and pill counts
- Assess signs and symptoms

### **Safety Labs**

- CBC with differential, platelet count
- BUN, Creatinine, electrolytes (including sodium, potassium, chloride, carbon dioxide/bicarbonate), liver function tests [including ALT, AST, bilirubin, SAP]
- Urine pregnancy test if applicable (of child bearing potential)

### **Research Labs and Procedures**

- Immunophenotyping to include CD4 count and cellular markers of activation (including CD4 count, HLA DR, CD38, co-expression of HLA DR and CD38 on CD4+ and CD8+ cells)
- Single copy assay & HIV-1 RNA levels
- Markers of bacterial translocation (LPS, bacterial 16S rDNA/bacterial RNA, sCD14)
- Soluble markers of inflammation (IL6, hsCRP, TNF $\alpha$ , D-dimer)
- Colonoscopy with gut biopsies is optional

### **Sample Storage**

- Stool storage for fecal microbiome analysis
- Sample storage

All subjects undergoing a colonoscopy at the end of phase 1 will receive a follow up phone call within 2 business days of their colonoscopy to ensure their safety.

## 5.5 Washout Phase

All participants will undergo a washout phase following phase 1. The washout period is 4 weeks in duration. If the participant requires a vaccination, the vaccine will be administered as early in the washout period as possible, and the washout period will be extended to a total of six weeks. If the patient requires antibiotics or systemic steroids during the course of the washout period, the washout period will be extended by 4 weeks after the completion of the antibiotics or steroids.

## 5.6 Treatment Phase 2

Subjects initially randomized to rifaximin will switch to the placebo arm, while subjects initially randomized to the placebo arm will switch to the rifaximin arm.

### Day 0, Phase 2

#### General Procedures

- Targeted history and physical examination as medically indicated
- Adherence counseling and pill counts
- Assess signs and symptoms

#### Safety Labs

- CBC with differential, platelet count
- BUN, Creatinine, electrolytes (including sodium, potassium, chloride, carbon dioxide/bicarbonate), liver function tests [including ALT, AST, bilirubin, SAP]
- Urine pregnancy test if applicable (of child bearing potential)

#### Research Labs

- Immunophenotyping to include a CD4 count and cellular markers of activation (including HLA DR, CD38, co-expression of HLA DR and CD38 on CD4 and CD8 cells)
- Single copy assay and HIV-1- RNA levels
- Soluble markers of inflammation (IL6, hsCRP, TNF $\alpha$ , D-dimer)
- Markers of bacterial translocation (LPS, bacterial 16S rDNA/bacterial RNA, sCD14)

#### Sample Storage

- Stool sample for fecal microbiome
- Sample storage

### Day 3, Phase 2 (optional visit)

#### General Procedures

- Targeted history and directed physical examination as medically indicated
- Adherence counseling and pill counts
- Assess signs and symptoms

### **Safety Labs**

- Urine pregnancy test if applicable (of child bearing potential)

### **Research Labs**

- CBC with differential
- Immunophenotyping to include a CD4+ count and cellular markers of activation (including HLA DR, CD38, co-expression of HLA DR and CD38 on CD4+ and CD8+ cells)
- Single copy assay & HIV-1 RNA levels
- Soluble markers of inflammation (IL6, hsCRP, TNF $\alpha$ , D-dimer)

### **Sample Storage**

- Stool storage for fecal microbiome analysis

### **Day 7, Phase 2+/- 3 days**

#### **General Procedures**

- Targeted history and directed physical examination as medically indicated
- Adherence counseling and pill counts
- Assess signs and symptoms

### **Safety Labs**

- Urine pregnancy test if applicable (of child bearing potential)

### **Research Labs**

- CBC with differential
- Immunophenotyping to include a CD4+ count and cellular markers of activation (including HLA DR, CD38, co-expression of HLA DR and CD38 on CD4+ and CD8+ cells)
- Single copy assay & HIV-1 RNA levels
- Markers of bacterial translocation (LPS, bacterial 16SrDNA/bacterial RNA, sCD14)
- Soluble markers of inflammation (IL6, hsCRP, TNF $\alpha$ , D-dimer)

### **Sample Storage**

- Stool storage for fecal microbiome analysis
- Sample storage

## **Day 14, Phase 2 +/- 3 days**

### **General Procedures**

- Targeted history and directed physical examination as medically indicated
- Adherence counseling and pill counts
- Assess signs and symptoms

### **Safety Labs**

- Urine pregnancy test if applicable (of child bearing potential)
- PT/INR

### **Research Labs**

- CBC with differential
- Immunophenotyping to include a CD4+ count and cellular markers of activation (including HLA DR, CD38, co-expression of HLA DR and CD38 on CD4+ and CD8+ cells)
- Single copy assay & HIV-1- RNA levels
- Markers of bacterial translocation (LPS, bacterial 16SrDNA/bacterial RNA, sCD14)
- Soluble markers of inflammation (IL6, hsCRP, TNF $\alpha$ , D-dimer)

### **Sample Storage**

- Stool storage for fecal microbiome analysis
- Sample storage

## **Day 28, Phase 2, +/- 3 days**

### **General Procedures**

- Targeted history and physical examination as medically indicated
- Adherence counseling and pill counts
- Assess signs and symptoms

### **Safety Labs**

- CBC with differential, platelet count
- BUN, Creatinine, electrolytes (including sodium, potassium, chloride, carbon dioxide/bicarbonate), liver function tests [including ALT, AST, bilirubin, SAP]
- Urine pregnancy test if applicable (of child bearing potential)

### **Research Labs and Procedures**

- Immunophenotyping to include a CD4 count and cellular markers of activation (including HLA DR, CD38, co-expression of HLA DR and CD38 on CD4 and CD8 cells)
- Single copy assay & HIV-1 RNA levels
- Soluble markers of inflammation (IL6, hsCRP, TNF $\alpha$ , D-dimer)

- Markers of bacterial translocation (LPS, bacterial 16S rDNA/bacterial RNA, sCD14)
- Colonoscopy with gut biopsy is optional

### **Sample Storage**

- Stool sample for fecal microbiome
- Storage
- All subjects undergoing a colonoscopy at the end of phase 2 will receive a follow up phone call within 2 business days of their colonoscopy to ensure their safety.

## **Final Visit +/- 2 weeks**

### **General Procedures**

- Targeted history and physical examination as medically indicated
- Assess signs and symptoms

### **Safety Labs**

- CBC with differential, platelet count
- BUN, Creatinine, electrolytes (including sodium, potassium, chloride, carbon dioxide/bicarbonate), liver function tests [including ALT, AST, bilirubin, serum SAP]
- Urine pregnancy test if applicable (of child bearing potential)

### **Research Labs**

- Immunophenotyping to include a CD4 count and cellular markers of activation (including HLA DR, CD38, co-expression of HLA DR and CD38 on CD4 and CD8 cells)
- Single copy assay & HIV-b-DNA assay)
- Soluble markers of inflammation (IL6, hsCRP, TNF $\alpha$ , D-dimer)
- Markers of bacterial translocation (LPS, bacterial 16S rDNA/bacterial RNA, sCD14)

### **Sample Storage**

- Stool sample for fecal microbiome
- Sample storage

## **5.7 Study-Related and Non-Study Related Procedures and Vaccinations**

Routine vaccinations (i.e. influenza) may be administered during the screening process or washout phase. Subjects receiving routine vaccinations during the washout phase will have their washout extended to 6 weeks. At each of these visits subjects will undergo interim evaluation of symptoms by study personnel and a targeted physical examination as deemed medically appropriate. Samples for the study are shipped from the University of Pittsburgh, NIH and Walter Reed sites to NCI for analysis. In the event of unforeseen logistical circumstances (e.g., because of a flight delay in sample shipment) resulting in a loss of samples necessary for analysis of the primary endpoint, and if the participants have already started phase 1 or 2 drug/placebo in

the interim, the participants will be asked to stop taking drug/placebo. They will undergo a four week washout and restart the respective study phase.

Gut mucosal biopsies via colonoscopy are optional and, if done, will be performed at baseline and upon completion of the rifaximin dosing and the placebo dosing phases (Days 28 of phases 1 and phase 2). If a subjects opts in for two of the three colonoscopies, these will be performed on approximately day 28 of phases 1 and 2, if a subjects opts for a single colonoscopy it will be performed on approximately day 28 of phase 2 of the study to maintain uniformity. As the relative representation of mucosal immunophenotypes and HIV-1-RNA levels can vary according to the location of the sampling site [61], multiple biopsies will be obtained during colonoscopy from the distal ileum and rectosigmoid (a total of 60 biopsies). For subjects enrolled at the NIH gut biopsies will be conducted under protocol 95-I-0027 entitled "Virologic and Immunologic Evaluation of Lymph Node, Tonsillar and Intestinal Biopsies, and Bronchoalveolar Lavage Fluid," as this protocol was designed to serve as a mechanism to obtain tissue samples.

All subjects in whom a colonoscopy is to be performed will be instructed to abstain from receptive anal intercourse for 3 days prior to rectal biopsy, and for 7 days post-biopsy to minimize risk of bleeding complications. Participants also should abstain from administration of rectal medications (including over-the-counter medications) for 3 days prior to rectal biopsies. All visits during the dosing phases will be completed on the indicated days of the protocol within a 3 day window. The washout phase may be extended from 4 to 6 weeks if necessary (i.e., immunizations, transportation, etc.). The final study visit may be completed +/- 2 weeks of anticipated study completion.

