### **4.3 Study Products**

#### **Drug:**

Description- Rifaximin capsules for oral administration

Dosing and Administration- 550 mg will consist of three capsules to be taken twice a day.

Route of Administration- Oral

Duration of Therapy- 28 days (56 doses)

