**TABLE 1: Schedule of Events**

Procedures	SCREENING			STUDY PHASE 1						STUDY PHASE 2					
	Screen # 1	Screen # 2	Gut Bio psy	Day 0	Day 3 (optional)	Day 7	Day 14	Day 28	Wash-out	Day 0	Day 3 (optional)	Day 7	Day 14	Day 28	Final visit
Window			-30 day			+/- 3 days	+/- 3 days	+/- 3 days	+2 weeks			+/- 3 days	+/- 3 days	+/- 3 days	2 wks
Informed Consent	X														
Complete history and physical*		X													
HIV testing if needed	X														
Safety Labs **															
PT/INR		X					X						X		
CBC w/differential, platelet count		X		X	X	X	X	X		X	X	X	X	X	X
BUN, Cr, electrolytes, LFTs		X		X				X		X				X	X
Urine pregnancy test if applicable/Urine analysis%		X		X	X	X	X	X		X	X	X	X	X	X
Hepatitis profile@		X													
Research related labs															
Immunophenotyping		X		X	X	X	X	X		X	X	X	X	X	X
HIV- 1- RNA level	X	X		X	X	X	X	X		X	X	X	X	X	X
Single copy assay	X	X		X	X	X	X	X		X	X	X	X	X	X
Soluble biomarkers of inflammation***		X		X	X	X	X	X		X	X	X	X	X	X
Markers of bacterial translocation#		X		X		X	X	X		X		X	X	X	X
Colonoscopy and gut biopsy\$			X					X						X	
General Processes															
Adherence counseling; pill counts		X		X	X	X	X	X		X	X	X	X	X	
Assessment of symptoms, targeted	X	X		X	X	X	X	X		X	X	X	X	X	X

history and physical ^															
Cross-over (treatment arms)									X						
Study product dispensing				X						X					
Sample Storage															
Sample storage		X		X		X	X	X		X		X	X	X	X
Stored Stool for fecal microbiome				X	X	X	X	X		X	X	X	X	X	X

Footnotes

- \*Comprehensive history and physical examination will be performed at screening visit 2
- \*\* Abnormal safety labs will be confirmed before subjects are excluded
- \*\*\* highly sensitive C reactive protein (hsCRP), D-dimer, interleukin-6 (IL-6), tumor necrosis factor alpha (TNF- $\alpha$ )
- ^interim assessments; physical exam as warranted
- # Plasma LPS, bacterial 16S rDNA, sCD14
- \$ Colonoscopy is optional and will be performed at baseline and upon completion of the rifaximin treatment and placebo treatment phases. The baseline colonoscopy can be performed in the 30 days prior to day 0. While those being performed at the end of the treatment phases, must be completed while the subject is on study drug/placebo and can be completed in the 3 days prior to the completion of drug/placebo.
- % If clinically indicated

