### 12.3 Description of the Statistical Methods

This is a double-blind, randomized, crossover placebo-controlled trial of rifaximin use in aviremic HIV-infected subjects.

The primary goal of this study is to compare the sCD14 levels during the rifaximin and placebo phases of the study. Patients who receive steroids or an additional antibiotic during a treatment period will have a pause and then restart the treatment for a complete period (as described on page 29). Thus such patients will have the endpoints measured at the end of each of the two periods and will be included in the primary analysis. A sensitivity analysis will be conducted where such patients are excluded.

Forty-four aviremic subjects will be randomized to either rifaximin followed by placebo or placebo followed by rifaximin (22 per sequence). The following table displays the treatment and control sequence for the study.

Treatment phase 1	Washout	Treatment phase 2
Day 0-28		Day 0-28
22 aviremic subjects receive rifaximin initially	Washout	22 aviremic subjects switch treatment assignments and receive placebo.
22 aviremic subjects receive placebo initially	Washout	22 aviremic subjects switch treatment assignments and receive rifaximin

At the end of this trial, one sample Wilcoxon statistic will be applied to evaluate the primary end points (difference on Days 28 of treatment phase 1 and 2 of the study). The primary endpoints of interest are changes in soluble CD14 levels between the rifaximin and placebo phases of the study. A P value less than 0.05 will be used to claim significance [114]. Statistical tests and confidence intervals will be two sided.

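### The Day 28 window lets the primary sCD14 sample be drawn up to about 2.5 days after the last dose, while the optional colonoscopy at the same visit must be done on study product

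*Combined protocol and SAP*

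**What the plan says.** **Dosing.** At the randomization visit (section 5.2), "subjects will be asked to initiate study drug the day after randomization is complete". Section 4.3 fixes the course: "Duration of Therapy- 28 days (56 doses"), with "550 mg will consist of three capsules to be taken twice a day". The placebo course has the same length. Section 5.6 does not repeat the day-after start rule for phase 2.

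**Visit window.** Sections 5.4 and 5.6 and Table 1 give the Day 28 visit a symmetric window; the phase 2 heading reads "Day 28, Phase 2, +/- 3 days". Section 5.7 states the general rule: "All visits during the dosing phases will be completed on the indicated days of the protocol within a 3 day window".

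**What the visit supplies.** The Day 28 research labs include "Markers of bacterial translocation (LPS, bacterial 16S rDNA/bacterial RNA, sCD14"). Section 12.3 takes this time point as primary: "primary end points (difference on Days 28 of treatment phase 1 and 2 of the study").

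**The on-drug rule.** The colonoscopy footnote to Table 1 says that end-of-phase procedures "must be completed while the subject is on study drug/placebo and can be completed in the 3 days prior to the completion of drug/placebo". This rule covers only the optional colonoscopy. The protocol does not require the Day 28 blood to be drawn on study product, does not provide doses beyond the 56 for a late visit, and does not say how a sample drawn after the last dose enters the primary analysis.

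**The concern.** The primary contrast is meant to compare sCD14 at the end of four weeks on rifaximin with sCD14 at the end of four weeks on placebo. On three of the seven permitted visit days, the subject has already finished the course. A late placebo-phase sample loses nothing, because there is no drug effect to fade. A late rifaximin-phase sample may catch an effect in decline. Using the same window in both phases does not cancel this, and blinding prevents selective timing but not dilution.

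The protocol applies an on-drug rule to an optional, exploratory procedure at this visit, yet leaves the mandatory primary sample without one. Once collected, an off-drug sample cannot be corrected, and without the time of the last dose it cannot be reliably identified.

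**Working it through.** **1. Dose clock.** Inputs: first dose on Day 1 (section 5.2), 56 doses twice daily (section 4.3; 28 × 2 = 56), window Days 25 to 31 (sections 5.4, 5.6, 5.7 and Table 1). Doses 12 hours apart at 8:00 and 20:00 are my assumption.

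- Morning first dose on Day 1: dose 56 comes 55 × 12 h = 27.5 days later, on the evening of Day 28.
- Visits at 8:00 on Days 29, 30 and 31 then fall 0.5, 1.5 and 2.5 days after the last dose. A visit at 16:00 on Day 31 gives 2.8 days.
- Evening first dose on Day 1: the Day 31 gap is 2.0 to 2.3 days.
- If phase 2 dosing began on Day 0, which section 5.6 does not exclude, the Day 31 gap would be 3.0 to 3.8 days.
- Under the Day 1 start, a visit on Day 28 itself is still on drug. At the early edge, a Day 25 sample follows about 24 days of dosing.

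**2. The plan's power figure.** Section 12.2 gives SD 0.45, correlation 0.71, difference 0.20 (all sCD14 values × 10⁶ pg/mL), n = 40, type I error 0.05 and a paired t test; section 12.3 makes tests two-sided.

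- SD of the difference = 0.45 × √(2 × (1 − 0.71)) = 0.343
- Noncentrality = √40 × 0.20 / 0.343 = 3.69
- Power from the noncentral t with 39 df = 94.9%, which reproduces the stated 95%. With 44 pairs it is 96.6%.

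Section 12.3 plans a Wilcoxon test. I keep the t test because it is the basis of the plan's own figure.

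**3. Illustration of dilution.** The documents give no sCD14 offset rate and no distribution of visit days. Assumptions: rifaximin-phase visits spread evenly over Days 25–31 (3/7 after the last dose); full effect while on drug; exponential decay with half-life h days afterwards.

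- Retained fraction f = 1 − (3/7) × (1 − mean of 2^(−g/h)), with g = 0.5, 1.5, 2.5
- For h = 7: the mean of 0.952, 0.862 and 0.781 is 0.865, so f = 1 − (3/7)(0.135) = 0.942
- For h = 14: the mean of 0.975, 0.928 and 0.884 is 0.929, so f = 0.970

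| Half-life | Mean effect (0.20 × f) | Power, n = 40 | Power, n = 44 |
|---|---|---|---|
| no fading | 0.200 | 94.9% | 96.6% |
| 14 days | 0.194 | 93.7% | 95.6% |
| 7 days | 0.188 | 92.4% | 94.6% |

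Half-lives of 4 and 2 days would give mean effects of 0.181 and 0.167 and power of 90.3% and 85.3% at n = 40, but nothing in the documents supports offset that fast. To show how far the even spread matters: if half of the rifaximin-phase samples were drawn 2.5 days late, power at n = 40 would be 92.4% (14 days) or 89.3% (7 days).

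**The case against.** **Size.** The only offset information in the documents is in section 3.1: gut microbial groups return to initial values after about four weeks of washout. That concerns ulcerative colitis patients and an upstream marker, but it points to slow rather than fast offset. The even visit spread is also assumed, and 2.5 days is a permitted maximum, not an expected delay. This stands. It limits the plausible loss to about 1 to 3 points of power.

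**Headroom.** The Protocol Summary plans 44 subjects completing both phases, and section 10.8 replaces those who discontinue. On that reading, slow offset leaves power at about the stated 95%. Section 12.2, however, counts 44 as accrual with 10% loss, so the headroom depends on which statement governs.

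**The narrower window has costs.** If the effect also builds slowly, samples on Days 25–27 precede its Day 28 level. With a 14-day half-life for both onset and offset, the change lifts power at n = 40 only from about 93% to about 94%. Discarding late samples would undo that: two lost pairs (n = 38) give 93.9%. Late samples should therefore stay in the primary analysis.

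**Stronger readings that the text does not support.** A reader might infer that the window separates blood, stool and tissue meant to describe one drug state. Section 6.2 requires stool to be collected before the bowel preparation, so in colonoscopy subjects, whose procedure must be on drug, the stool is on drug too. Nothing forbids an on-drug biopsy and off-drug blood six days apart, but sections 5.4 and 5.6 list both under one visit. A reader might also infer that late sampling must always shrink the estimate. That holds only if the effect fades after the last dose, which the documents do not establish.

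**Conclusion.** The gap is real and follows from the text: the primary sCD14 sample may be drawn up to about 2.5 days after the last dose under the stated phase 1 start, while the on-drug rule covers only the optional colonoscopy at the same visit. The consequence is possible dilution of the primary contrast. It is not a threat to the type I error.

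Its likely size is small: about 1 to 3 points of power at n = 40 for half-lives of 7 to 14 days, and about 95–96% power remaining with 44 completers. These figures rest on an assumed even visit spread and an assumed decay; slower offset would make the loss negligible. The conclusion that the window and the footnote should be aligned does not depend on them. This is a cheap improvement, not a flaw that undermines the trial.

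**What to change.** - In sections 5.4, 5.6 and 5.7 and in Table 1, set the Day 28 research blood window to −3/+0 days in both phases, and state that the sample is taken while the subject is on study product, as the colonoscopy footnote already requires.
- Record the date and time of the last dose and of the sample. The pill counts in section 4.5 give only partial information. The recorded times would also show any off-drug sample arising because section 5.6 does not state the phase 2 start day.
- In section 12.3, keep any late sample in the primary analysis so that no pairs are lost, and add a sensitivity analysis that excludes samples drawn after the last dose.

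Dosing is unchanged, and no extra visits, samples or subjects are needed. The cost is protocol wording, two recorded times per phase, and slightly harder scheduling: four permitted days instead of seven.
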